16.3 Pharmacokinetic Concentrations

Plasma concentrations below the quantifiable limit (BQL) will be set to 0 in the computation of concentration summary statistics.

Descriptive statistics, including number (N), number for higher or equal values of Lower Limit of quantification ($N \geq \text{LLOQ}$), arithmetic mean, standard deviation (SD), coefficient of variation (%CV), standard error of the mean (SEM), minimum, median, maximum, and geometric mean will be used to summarize the plasma concentrations at each scheduled time point. As BQL results are set to 0, statistics will be calculated with 0 for BQL results, i.e. minimum will be displayed as 0, and the respective patient will be included in counting the number of patients with results, but excluded in counting the number of patients with higher or equal values of LLOQ. Zero concentrations will be considered as missing in geometric mean calculations. If more than half of the patients have values BQL, the summary descriptive statistics will not be performed for that time point.

Linear and semi-logarithmic plots of the arithmetic mean (\pm SD) plasma concentration by scheduled sampling time will be provided. These plots will show time in hours. The plots will match the summary table results and will not have an observation at a given time point if more than half of the patients have values BQL.

Linear and semi-logarithmic plots of the individual plasma concentration by actual sampling time will be provided by patient (one patient per page). These plots will show time in hours. In individual plots concentrations BQL will not be shown.

All individual patient plasma concentration data will be listed.

16.4 Statistics of Pharmacokinetic Parameters

Statistical analyses will be performed to assess the effect of steady-state itraconazole and rifampin on the PK of pamiparib using the treatment in combination with pamiparib as test and the treatment with pamiparib only as reference.

Summary statistics will include number (N), arithmetic mean, standard deviation (SD), %CV, standard error of the mean (SEM), minimum, median, maximum, and geometric mean. For T_{\max} , only n, median, min and max will be presented.

Data for each treatment part will be analyzed separately.

A linear mixed model with a fixed effect for treatment and a random effect for patient will be used on the natural log-transformed parameters C_{\max} , $AUC_{0-\text{last}}$, and $AUC_{0-\text{inf}}$. A point estimate and the corresponding 90% CI for the difference between least squares means of Test and Reference treatment (Test – Reference) will be calculated. The antilogarithm of this value will be calculated to obtain the point estimate and the 90% CI for the ratio (Test/Reference) of the geometric means on the untransformed scale. For each

parameter selected for analysis, patients who do not have valid parameters in both periods will not be included for analysis.

The SAS PROC MIXED code is as follows:

```
proc mixed data = adpp;  
  by parameter;  
  class treatment patient;  
  model ln(aval) = treatment;  
  random patient;  
  lsmeans treatment / alpha = 0.1;  
  estimate "Pamiparib only vs Pamiparib with Itraconazole/Rifampin"  
  treatment -1 1 / e cl alpha=0.1;  
run;
```

For parameters C_{max} , AUC_{0-last} , and AUC_{0-inf} a listing of the individual patient ratios (Test/Reference) will be provided.

A forest plot of the geometric LS mean ratios of C_{max} , AUC_{0-last} , and AUC_{0-inf} will be provided for a visual representation of the data.

All plasma PK parameters will be listed by patient.

17.0 Tumor Assessment

Tumor identification and assessment will be listed..

18.0 Safety Analyses

18.1 Safety Variables

The following safety variables will be summarized:

- Adverse Events (AEs)
- Vital Signs, including weight
- Electrocardiograms (ECG)
- Clinical Laboratory Evaluations

All summaries will be by treatment within a part/treatment arm.

18.1.1 Adverse Events

Adverse events will be classified using the Medical Dictionary for Regulatory Activities (MedDRA) classification system.

All adverse events (including non-treatment-emergent events) recorded on the CRF will be listed.

All AE summaries will include only treatment-emergent adverse events. Treatment-emergent adverse events are those AEs with an onset date on or after the date of first dose of study medication until the date of last study medication dose plus 30 days.

AEs will be categorized according to the following:

- Prior to Day 1 (thus not summarized, just listed)
- From Day 1 to the day prior to start rifampin or itraconazole dosing (category = pamiparib only)
- Part A: The day of start of rifampin dosing to the day prior to combined pamiparib and rifampin dosing (category = rifampin)
- Part A: At or after the day of coadministration until date of last dosing in core phase plus 30 days and before the administration of pamiparib in the Extension Phase (category = pamiparib with rifampin)

- Part B: The day of start of itraconazole dosing to the day prior to combined pamiparib and itraconazole dosing (category = itraconazole)
- Part B: At or after the day of coadministration until date of last dosing in core phase plus 30 days and before the administration of pamiparib in the Extension Phase (category = pamiparib with itraconazole)
- Extension Phase AEs

An overview of all AE will present the following frequencies by treatment and part:

- All treatment-emergent AEs
- Grade 3 or greater treatment-emergent AEs
- Treatment-related, treatment-emergent AEs
- Serious treatment-emergent AEs
- Serious, treatment-related treatment-emergent AEs
- Treatment-emergent AEs with an outcome of death
- Treatment-emergent AEs leading to discontinuation of study treatment

A breakdown of the number and percentage of patients reporting each adverse event, categorized by body system and preferred term, will be presented. Counting will be done by patient only, not by event; patients will only be counted once within each body system or preferred term.

A summary of drug related events reported, categorized by relationship to either study drug, will be provided. Patients with multiple events within a particular body system or preferred term will be counted once for a relation to study drug within that body system or preferred term.

A summary of events reported, categorized by toxicity grade (CTCAE version 5.0), will be provided. If a patient experiences multiple occurrence of the same AE with different intensity toxicity grades, the patient will be counted once for the maximum (most severe) toxicity grade. AEs with a missing intensity will be presented in the summary table with a toxicity grade of "Missing". For each toxicity grade, the number and percentage of patients with at least 1 treatment emergent AE of the given grade will be summarized.

A listing of adverse events leading to treatment discontinuation will be provided.

The following missing data will be imputed as defined (for calculations only / will not be presented):

- Missing AE start times for the determination of treatment emergence will be assumed to occur after treatment unless partial date documents the AE as happening prior to treatment
- Missing or partial AE start date will be assumed to be after treatment for the determination of TEAE unless the start or end date is prior to treatment

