9.1 Adverse Events

9.1.1 Definition and Reporting of an Adverse Event

An AE is defined as any unfavorable and unintended sign (including an abnormal laboratory finding), symptom, or disease (new or exacerbated) temporally associated with the use of a study drug, whether considered related to study drug or not.

Examples of AEs include:

- Worsening of a chronic or intermittent pre-existing condition including an increase in severity, frequency, duration, and/or has an association with a significantly worse outcome
- New conditions detected or diagnosed after study drug administration even though it may have been present before the start of the study
- Signs, symptoms, or the clinical sequelae of a suspected interaction
- Signs, symptoms, or the clinical sequelae of a suspected overdose of either study drug or a concurrent medication (overdose per se should not be reported as an AE or SAE)

When an AE or SAE occurs, it is the responsibility of the investigator to review all documentation (eg, hospital progress notes, laboratory results, and diagnostics reports) relative to the AE or SAE. The investigator will then record all relevant information regarding an AE or SAE in the eCRF. However, there may be instances when copies of medical records for certain cases are requested by the sponsor. In this instance, all patient identifiers will be blinded on the copies of the medical records prior to submission to the sponsor.

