9.1.4 Follow-Up of Adverse Events

After the initial AE or SAE report, the investigator is required to proactively follow each patient and provide further information to the sponsor on the patient's condition.

All AEs and SAEs documented at a previous visit/contact and designated as ongoing will be reviewed at subsequent visits/contacts.

All AEs and SAEs will be followed until resolution, the condition stabilizes or is considered chronic, the AE or SAE is otherwise explained, the patient is lost to follow-up, or the patient withdraws consent. Once resolved, the appropriate AE or SAE eCRF page(s) will be updated. The investigator will ensure that follow-up includes any supplemental investigations as may be indicated to elucidate the nature and/or causality of the AE or SAE. This may include additional laboratory tests or investigations, histopathologic examinations, or consultation with other health care professionals.

The sponsor may request that the investigator perform or arrange for the conduct of supplemental measurements and/or evaluations to elucidate as fully as possible the nature and/or causality of the AE or SAE. The investigator is obligated to assist. If a patient dies during participation in the study or during a recognized follow-up period, the sponsor will be provided with a copy of any postmortem findings, including histopathology, if conducted.

New or updated information will be recorded on the originally completed SAE report/eCRF, with all changes SAE form changes signed and dated by the investigator. The updated SAE follow-up report/eCRF should be re-sent to the sponsor within the time frames outlined in [Section 9.5.1](#).

If a patient is lost to follow-up, study center personnel must do their utmost to re-establish contact with the patient. All measures taken to follow up with the patient should be recorded.

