9.2.2 Treatment/Patient Grouping

Treatment emergent Adverse events (TEAEs) will be summarized by the last treatment received, i.e. "Treatment at onset"

The following treatment labels will be used for the core phase:

Part/Treatment Arm	Treatment Label	Dosing	Used for assessments done at
A	'Pamiparib only'	60 mg single dose	Day 1 - 2
A	'Rifampin'	600 mg QD	Day 3 - 9
A	'Pamiparib with Rifampin'	60 mg and 600 mg	Day 10 - 12
B	'Pamiparib only'	20 mg single dose	Day 1 - 2
B	'Itraconazole'	200 mg QD	Day 3 - 6
B	'Pamiparib with Itraconazole'	20 mg and 200 mg	Day 7 - 9

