9.2.3 Other Definitions

General definitions for variables as used in the text.

Change from baseline will be calculated for safety measures, see below.

Variable	Dataset	Definition/Calculation
Change from Baseline	All	Post-dose Observation minus Baseline Observation
Study Day (Prior to first dose day)	All	Date of Measurement minus Dose Date
Study Day (Predose on first dose day and post first dose)	All	Date of Measurement minus Dose Date +1
TEAE	AE	AE is a TEAE if the AE with an onset date on or after the date of first dose of study medication until the date of last study medication dose plus 30 days.

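### The SAP places adverse events in treatment columns by onset date alone and has no rule for an event whose grade rises in a later period

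*SAP*

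**What the plan says.** Four SAP rules decide where an adverse event appears and at what grade.

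- **Treatment emergence.** SAP 18.1.1: "Treatment-emergent adverse events are those AEs with an onset date on or after the date of first dose of study medication", up to 30 days after the last dose. The definitions table in SAP 9.2.3 repeats the onset test, with the same 30-day end point: "AE is a TEAE if the AE with an onset date on or after the date of first dose of study medication until the date". Neither mentions a rise in grade.
- **Column.** SAP 9.2.2 says that TEAEs "will be summarized by the last treatment received, i.e". It glosses this as the treatment at onset.
- **Windows.** The periods in SAP 18.1.1 do not overlap. The coadministration category runs "until date of last dosing in core phase plus 30 days and before the administration of pamiparib in the Extension Phase", and Extension events form their own category.
- **Grade.** Where a patient has several occurrences of the same event at different grades, "the patient will be counted once for the maximum (most severe) toxicity grade".

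On recording, Protocol 9.1.1 gives as an example of an AE: "Worsening of a chronic or intermittent pre-existing condition including an increase in severity". Protocol 9.1.4 has ongoing events reviewed at later contacts and adds: "Once resolved, the appropriate AE or SAE eCRF page(s) will be updated". For SAEs, the same section has new information entered on the original report. Protocol 5.6 and 10.1 leave data entry to eCRF completion guidelines, which are not part of the two documents.

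**The concern.** Both secondary objectives are about safety by period: pamiparib given with rifampin or itraconazole, and pamiparib in the Extension. The tables serve them only if each column shows what happened in that period.

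Events that cross a boundary are foreseeable. The Core windows in SAP 9.2.2 are short: Days 1-2, then Days 3-9 and 10-12 in Part A, or Days 3-6 and 7-9 in Part B. The Extension can follow soon after, since Protocol 4.1 lets the Core End-of-Treatment assessments serve as the Extension predose visit. Nausea (64.4%) and fatigue (33.3%) were common in the first-in-human study (Protocol 1.2.1.3), and such events can persist and change in grade.

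If a worsening event keeps its first onset date, the earlier column carries a severity that arose under a later treatment, and the later column loses the event. Part B shows the problem most clearly. Coadministration there uses a single 20 mg dose, while the Extension uses 60 mg twice daily. Toxicity that becomes severe under continuous dosing could be read as a safety signal for the itraconazole combination.

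**Working it through.** The plan gives no figure on this point, so there is none to reproduce. The check applies the SAP 18.1.1 windows to a hypothetical event that rises from Grade 1 to Grade 3 across a boundary, under two recording conventions.

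**Inputs**
- Part A windows by onset day: pamiparib only, Days 1-2; rifampin, Days 3-9; pamiparib with rifampin, Day 10 until the first Extension dose.
- Part B windows: pamiparib only, Days 1-2; itraconazole, Days 3-6; pamiparib with itraconazole, Day 7 until the first Extension dose.
- Extension start: Day 19 in Part A and Day 16 in Part B. Both are assumptions. Any start after the onset day and no later than the day of worsening gives the same result.
- Under the one-record convention, the record keeps its first onset date and carries the highest grade reached. This too is an assumption.

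**Results**

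| Case | Grade 1 onset | Grade 3 reached | One record | New record when the grade rises |
|---|---|---|---|---|
| Part A, within Core | Day 2 | Day 10 | Grade 3 under pamiparib only; nothing under pamiparib with rifampin | Grade 1, then Grade 3 under pamiparib with rifampin |
| Part B, within Core | Day 2 | Day 7 | Grade 3 under pamiparib only; nothing under pamiparib with itraconazole | Grade 1, then Grade 3 under pamiparib with itraconazole |
| Part A, into Extension | Day 11 | Day 30 | Grade 3 under pamiparib with rifampin; nothing under Extension | Grade 1, then Grade 3 under Extension |
| Part B, into Extension | Day 8 | Day 30 | Grade 3 under pamiparib with itraconazole; nothing under Extension | Grade 1, then Grade 3 under Extension |

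The same SAP rules therefore give opposite placements of the Grade 3 event, depending only on how the eCRF is completed.

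**Which convention applies?** The documents do not settle it. Protocol 9.1.4 points to updating the original record for SAEs. Its sentence on updating pages concerns resolution and not a grade increase. Protocol 9.1.1 accepts worsening as an AE, but its example is a pre-existing condition and not an on-study event. The grade rule in SAP 18.1.1 is written for multiple occurrences and fits either convention.

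**Size per patient.** SAP 6.1 plans about 12 enrolled and 10 completing in each part. One patient is 1/12 = 8.3% or 1/10 = 10% of a Core column.

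**The case against.** The strongest reply is that assignment by treatment at onset is an explicit, prespecified convention, and that it works correctly if a grade increase opens a new record. No sentence in either document says that a worsening non-serious event stays one record. A reader might infer from the 9.1.4 instruction on updating pages that it does, but that instruction applies once an event has resolved. This stands: the misplacement is conditional. It does not close the gap, because the tables depend on a convention that the SAP never states.

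Second, worsening of a baseline condition is largely covered already. Protocol 9.1.1 makes it an AE in its own right, so it can carry an on-treatment onset date. Protocol 9.3.1 has only SAEs reported before the first dose, so there is generally no earlier non-serious record to absorb it. This also stands. What remains is mainly the assignment between periods.

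Third, a reader might take anemia as the leading case. SAP 18.1.3 provides shift tables of the worst post-baseline CTCAE grade by treatment, using scheduled and unscheduled results and independent of AE onset, plus a listing of laboratory results of Grade 3 or higher. All AEs are listed as well. This narrows the problem to summary tables of events such as nausea and fatigue. Listings do not correct those tables.

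Finally, safety is descriptive, with no hypothesis testing (SAP 9.4.3). That limits the consequence, but the tables still have to describe the right period.

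**Conclusion.** The concern holds as a conditional one. The SAP has an onset-only rule for treatment emergence and for column assignment, and nothing carries an event into a later period when its grade rises. Unless the eCRF opens a new record at each grade increase, such an event is tabulated at its highest grade under the treatment at first onset and is absent from the later column, including the Extension.

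Each affected patient can move a Core column of 10-12 patients by about 8-10 percentage points. The effect is confined to the descriptive AE summaries. AE listings, laboratory shift tables and the PK analysis are unaffected.

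No overall size can be derived. A reader might combine the 26% of patients with related events of Grade 3 or higher in Protocol 1.2.1.3 with 20 Extension patients and an assumed share of Core onsets. The documents do not support that calculation. The 26% comes from a study covering 2.5 to 120 mg twice daily. Extension entry is optional and no Extension number is given, and nothing indicates what share of such events would begin in the Core Phase.

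**What to change.** - In SAP 9.2.3 and 18.1.1, define a TEAE as an AE that starts, or increases in CTCAE grade, on or after the first dose, keeping the existing 30-day end of the window.
- In SAP 9.2.2 and 18.1.1, state that each period, including the Extension, counts AEs that start or worsen in that period, at the highest grade reached in that period.
- In the eCRF completion guidelines, tell sites to open a new AE record when the grade rises, and state this convention in the SAP.

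The cost is SAP wording and one completion instruction. No visit or procedure is added. SAP 3.0 refers to a final CRF dated 19 Aug 2019; a new-record instruction should need no change to that form, whereas a new grade-change date field might. If data have already been entered, AE records that stayed open across a period boundary would need checking.

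The downside is that one event can appear in two period columns, which a footnote should explain. Within a column nothing is double-counted, because SAP 18.1.1 already counts patients and not events. This is a low-cost improvement to the safety tables.

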6.0 Study Design

This is an open-label, parallel-group, fixed-sequence study in male and female cancer patients. Part A will investigate the effect of CYP3A induction by rifampin on the single-dose PK of pamiparib, and Part B will investigate the effect of CYP3A inhibition by itraconazole on the single-dose PK of pamiparib.

The study consists of two phases: the Core Phase, which is divided into Part A and Part B, and the Extension Phase. A total of approximately 24 patients will be enrolled (approximately 12 in each part) to ensure that at least 20 patients (10 in each part) complete the study.

[figure not shown]
In Part A, all patients will receive the following treatments:

- Day 1 and Day 10: single oral doses of 60 mg pamiparib
- Days 3 to 11: oral doses of 600 mg rifampin once a day

In Part B, all patients will receive the following treatments:

- Day 1 and Day 7: single oral doses of 20 mg pamiparib
- Days 3 to 8: oral doses of 200 mg itraconazole once a day

After completing the Core Phase, patients may participate in the Extension Phase, in which they will receive pamiparib twice a day in 28-day cycles until progression of disease, unacceptable toxicity, withdraw consent, or any other reason for discontinuation.

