9.1.3 Descriptive Statistics

Unless otherwise indicated, continuous variables will be summarized with the following descriptive statistics: n (number of observations), (arithmetic) mean, standard deviation (SD), minimum (min) value, median, and maximum (max) value.

Where calculated, Geometric CV (%) = $\sqrt{\exp(S^2) - 1} \times 100$, where S^2 is the sample variance of PK parameters in the logarithmic scale.

Categorical data will be summarized with frequencies and percentages. Percentages by categories will be based on the number of patients exposed within a category of interest.

For categorical data the categories will be presented in the tables exactly as they appear in the CRF / Database. No data manipulation will be done for presentation purposes.

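### Core Phase adverse event percentages by treatment compare a 2-day window with one of up to 32 days and show no time at risk, so the coadministration column is expected to look worse whenever its window is longer

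*SAP*

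**What the plan says.** SAP 18.1.1 defines the Core Phase adverse event categories by onset date. The reference category runs "From Day 1 to the day prior to start rifampin or itraconazole dosing (category = pamiparib only". The coadministration category in each part runs "At or after the day of coadministration until date of last dosing in core phase plus 30 days" and stops at the first Extension dose. An event is treatment-emergent "until the date of last study medication dose plus 30 days".

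The dosing days are in SAP 6.0. Part A has pamiparib on Days 1 and 10 and "Days 3 to 11: oral doses of 600 mg rifampin once a day". Part B has pamiparib on Days 1 and 7 and itraconazole on Days 3 to 8.

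On presentation, SAP 18.1 states: "All summaries will be by treatment within a part/treatment arm". SAP 18.1.1 adds: "Counting will be done by patient only, not by event". SAP 9.1.3 sets the denominator: "Percentages by categories will be based on the number of patients exposed within a category of interest". SAP 15.0 summarizes duration of treatment for the Extension Phase only. Neither the SAP nor Protocol 11.4 plans patient-time, an exposure-adjusted rate or an equal-window display for Core Phase events.

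SAP 9.2.2 first says that events are summarized by the last treatment received. Its table then labels coadministration as Days 10-12 (Part A) and Days 7-9 (Part B), without the 30-day tail of 18.1.1.

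**The concern.** A percentage of patients with at least one event is a cumulative incidence: it can only rise as the window lengthens. Here the columns within a part have very different windows, and nothing in the tables tells the reader so.

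These patients have advanced cancer and may have events from their disease or other causes on any day. A longer coadministration window collects more of them. Safety of pamiparib given with rifampin or itraconazole is a stated secondary objective, and a reader will naturally set the coadministration column beside the pamiparib-only column. An excess there could be taken for a tolerability cost of the interaction when it reflects only longer observation.

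**Working it through.** The plan states no window length or event rate, so there is no figure to reproduce. Windows are counted in inclusive study days.

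**1. Windows on schedule**

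| Category | Part A | Part B |
|---|---|---|
| Pamiparib only | Days 1-2 = 2 days | Days 1-2 = 2 days |
| Rifampin or itraconazole only | Days 3-9 = 7 days | Days 3-6 = 4 days |
| Coadministration, maximum | Day 10 to Day 11+30 = 41: 32 days | Day 7 to Day 8+30 = 38: 32 days |

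The maximum ratio of coadministration to pamiparib-only time is 32/2 = 16.

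**2. What shortens the coadministration window**

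If Extension dosing starts k days after the last Core dose (k up to 30), the window is k+1 days.

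- Next day, k = 1: 2 days, equal to the reference.
- Core EOT visit reused as the Extension predose visit: Protocol 4.1 allows 7 days from last Core dose to EOT and 7 more to the first Extension dose. So k is at most 14 and the window at most 15 days.
- EOT visit not reused: no maximum gap is stated.
- New anticancer therapy ends event reporting (Protocol 9.3.1) and also shortens the window.

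**3. Expected percentages with no interaction**

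The daily risk p is an assumption. P(at least one event in d days) = 1 - (1-p)^d.

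| Assumed p per day | 2 days | 15 days | 32 days |
|---|---|---|---|
| 0.5% | 1.0% | 7.2% | 14.8% |
| 2% | 4.0% | 26.1% | 47.6% |
| 5% | 9.8% | 53.7% | 80.6% |

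For 12 patients at p = 2%, the expected counts are 12 x 0.040 = 0.5 and 12 x 0.476 = 5.7 (2 vs 32 days).

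**4. Sensitivity to the assumptions**

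- *Sparser detection after discharge.* Protocol 8.2.1 requires daily questioning only while patients are resident. Suppose recorded risk halves after the 3 resident days (Days 10-12 or 7-9). Then 1 - (1-p)^3 (1-p/2)^29 = 8.4%, 29.7% and 58.9% over 32 days.
- *An equal acute risk after each pamiparib dose.* With an assumed 30%, 1 - 0.70 (1-p)^d gives, for 2 vs 32 days, 30.7% vs 40.4%, 32.8% vs 63.3% and 36.8% vs 86.4%.

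**5. Patient-days with 12 patients**

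Pamiparib only: 12 x 2 = 24. Coadministration: 12 x 2 = 24 if all roll over the next day; 12 x 15 = 180 if all start at 14 days; 9 x 15 + 3 x 32 = 231 if nine start at 14 days and three never do; 12 x 32 = 384 if none enter the Extension.

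**6. Early stoppers**

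The pamiparib-only category ends only when rifampin or itraconazole starts. A patient who stops before Day 3 and does not enter the Extension has no Day 2 end. On one reading, that patient counts to Day 1+30 = 31, which is 31 days. One such patient among 12 moves the column from 24 to 11 x 2 + 31 = 53 patient-days.

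The rifampin-only and itraconazole-only categories end only at coadministration, so they have the same open end. A patient whose last dose is rifampin on Day 9 could count from Day 3 to Day 39 (37 days against 7). For itraconazole on Day 6 it is Day 3 to Day 36 (34 days against 4). Protocol 6.7 makes such cases possible: events that require a dose hold lead to discontinuation from the Core Phase.

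**The case against.** The strongest reply is that no comparison between these columns is planned. The objective is to evaluate safety under coadministration, the display is descriptive, SAP 9.4.3 rules out formal testing, and test-versus-reference language is used only for PK. Assigning events to the treatment at onset is an ordinary convention, and post-dose events must go somewhere. All events and exposure are listed, and the SAP also plans this: "A summary of drug related events reported, categorized by relationship to either study drug, will be provided". With about 12 patients per part, the windows could be rebuilt by hand.

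This limits the impact but does not remove it. Followed as written, the SAP puts cumulative incidences over windows of up to 16:1 side by side. The listings permit a recalculation, but none is planned. The relatedness summary does not equalize time.

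The size is also open to challenge, and this stands. All the risks are assumed. The 5% figure is high: it implies a 30-day risk of 1 - 0.95^30 = 78.5%. The percentages are for any event, so individual preferred-term rows would be lower.

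SAP 9.2.2 could be read as limiting coadministration to 3 days. However, its table is headed for assessments done on those days, and 18.1.1 is the specific rule for adverse events. The two still need to agree.

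A reader might infer that the coadministration column must come out higher unless everyone rolls over the next day. The documents do not support that. With so few patients the excess is an expectation. Prompt new anticancer therapy also shortens the window, and early stoppers can lengthen the pamiparib-only one.

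**Conclusion.** The concern holds in a limited form. On schedule, SAP 18.1.1 sets 2 days of pamiparib alone against at most 32 days of coadministration, in once-per-patient percentages with no Core Phase time at risk. Whenever the coadministration window is longer and there is any background risk, that column is expected to show more patients with events without an interaction. The direction does not need a constant daily risk; the size does, and it cannot be fixed from the documents. The range in the working, from 1.0% vs 14.8% to 9.8% vs 80.6%, depends on the assumed daily risk, the full 32 days and equal detection throughout. The gap is smaller with prompt rollover or weaker detection after discharge.

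A reader might go further and infer that the drug-interaction conclusion is biased. It is not: the primary PK analysis does not use these categories. Nor do the documents show that an observed excess would be wholly artefact. This is a cheap improvement to a descriptive secondary display, to be considered rather than required. Confidence is high on window lengths and direction, not on size.

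**What to change.** In SAP 18.1.1, keep the full coadministration category and make these additions:

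- Show patient-days at risk for every Core Phase adverse event column.
- Split coadministration by onset into (a) Days 10-11 in Part A or Days 7-8 in Part B, the same length as Days 1-2, and (b) later Core follow-up. If columns are compared, set (a) against pamiparib-only events with onset on Days 1-2.
- In the pamiparib-only, rifampin-only and itraconazole-only columns, show separately any events after the scheduled window end in patients who stop before the next treatment starts.
- Reconcile SAP 9.2.2 with 18.1.1 so that one rule governs adverse event assignment.
- Footnote that the windows differ, and that the 2-day columns equalize time only and still include direct rifampin or itraconazole events and fixed-sequence effects. State also that events found at the scheduled Day 12 (Part A) or Day 9 (Part B) laboratory tests, ECG and examination fall in (b). The schedule has no laboratory tests on Days 1-2.

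The cost is SAP wording, one split column, a patient-days row and footnotes. Onset and dosing dates are already needed for 18.1.1, so no new data are required. The downside is few events in the 2-day columns, with about 12 x 2 = 24 patient-days per part, so they will support only a cautious reading.
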